1.4 Dose Rationale and Risk/Benefits

Nitrite delivery by intravenous, inhaled and oral routes of administration has been shown to be safe, and the plasma nitrite levels achieved with each route have been shown by our group and others to cause favorable effects on cardiac hemodynamics that we expect to improve both symptoms and exercise capacity in patients with HFpEF, as will be tested in this study.

Intravenous nitrite administration reduces pulmonary capillary wedge pressures (PCWP) at rest (-3 mmHg, $p<0.0001$) and particularly during exercise (adjusted exercise values 19 ± 5 mm Hg vs. 28 ± 6 mm Hg; $p=0.0003$). Similar effects are observed on pulmonary artery (PA) pressures, and there was a greater increase in cardiac output reserve (all $p<0.01$). Plasma nitrite levels achieved with the intravenous formulation were 8.39 ± 1.88 μ M (Borlaug et al. *J Am Coll Cardiol* 2015; 66:1672–82). While our group has shown that nitrite reduces arterial stiffness (*J Am Coll Cardiol*. 2017;70(2):136-148.), there was no symptomatic hypotension or methemoglobinemia with intravenous nitrite in this study, and no adverse events.

Inhaled nitrite (Stage I): In Stage I of this trial, participants received a dose of inhaled nebulized nitrite 80 mg 3 times daily. Participants developing symptoms of intolerance could be down-titrated to 46 mg 3 times daily. The nebulizer route was difficult to use for many of the participants, and mindful of the neutral results of the INDIE trial (manuscript currently under review), the manufacturer of the inhaled nitrite compound discontinued manufacture. For this reason, we are switching to an oral route of administration of nitrite in Stage II of our study.

Oral nitrite (Stage II): Like inhaled nitrite, oral nitrite has been found to be safe, without significant adverse effects in Phase I studies. The bioavailability of oral nitrite is excellent (95%) and similar to intravenous formulations. High doses of nitrite have also been provided in several studies by oral route in the form of beet root juice. Nutraceutical preparations are currently being sold in health stores with levels of nitrite (12.7 mg per tablet) that are similar to what will be used in Stage II of our study.

As of July 31, 2017, a total of 84 subjects were enrolled in 8 clinical trials testing oral sodium nitrite conducted under [name] IND# 115926 at the University of Pittsburgh. Subjects enrolled are predominantly female (57%) and Caucasian (77%). Among the 8 clinical trials, 2 clinical trials have been completed; one is a Phase 1 study aimed to establish the pharmacokinetics, metabolism and interconversion of nitrate to nitrite, nitrite to nitric oxide, and interaction with Conjugated Linoleic Acid (cLA) to form nitro-fatty acids *in vivo* in healthy adult normal volunteers (Hughan et al. *Hypertension* 2017; published ahead of press, doi: 10.1161/HYPERTENSIONAHA.117.09016). The other is a Phase 2 open labeled study designed to assess the safety and feasibility of oral nitrite therapy on the changes in skeletal muscle bioenergetics and physical capacity in older heart failure patients.

Five Phase 2 studies are ongoing. Of the five active studies, 2 studies are in the patient population of overweight/obese adults with metabolic syndrome and hypertension, at risk for insulin resistance and endothelial dysfunction, one in adult obese asthmatics with metabolic syndrome, and another one in older HF patients, one in adult HFpEF patients aged ≥ 18 years and another one in older HFpEF patients aged ≥ 70 years. [name] group has also initiated

another Phase 1 nitrate study aimed to determine distinguishing features of the structure and function of the oral and gut microbiome in PH-HFpEF and controls.

The oral nitrite for Stage II of this study will be provided under the supervision of our collaborator, [name], is an internationally recognized leader in the basic and clinical science of the inorganic nitrate/nitrite/NO pathway. [name] has held an IND for sodium nitrite (IND # 70,411) for cardiovascular applications and currently has an approved IND for the use of sodium nitrite for lung transplant recipients (IND # 111,643). The cardiovascular IND involved the administration of sodium nitrite to 69 normal volunteers in 4 phase I-II clinical trials without observed adverse effects. This study will be performed under the IND held by the PI, allowing the FDA to cross reference the [name] current IND for the oral formulation.

[name] has also treated 11 subjects with sickle cell disease on this IND without observed adverse effects. The lower doses of nitrite used in these investigational treatment regimens – 60-120 mg daily, or 20-40% of the intravenous dose (300mg) used in the emergency treatment of cyanide poisoning – do not produce methemoglobin levels greater than 3% and have not been associated with clinically significant hypotension. There have been no adverse events noted in the 80 treated normal human volunteers and patients with sickle cell disease.

With 20 mg oral nitrite, there are modest reductions in blood pressure with no increase in heart rate (Hughan et al. *Hypertension* 2017; electronically published ahead of press, doi: 10.1161/HYPERTENSIONAHA.117.09016). Similar to our prior studies with inhaled and intravenous nitrite, oral nitrite was observed in this study to cause a very mild and clinically insignificant rise in plasma methemoglobin levels, with no patients developing levels >3%.

The effects of oral nitrite on central hemodynamics have not yet been examined, but given the similar plasma nitrite levels observed with oral administration (Figure 7) and modest reduction in blood pressures (Figure 8), we expect reductions in pulmonary artery and pulmonary capillary wedge pressure at rest and during exercise of roughly similar magnitude to what we have observed following intravenous and inhaled preparations.

Risk from Study Drug-Overview

Sodium nitrite (NO₂⁻) has vasodilating properties, and the most significant expected risk in this population would be symptomatic hypotension. NO₂⁻ is converted in vivo to nitric oxide (NO) and thus may cause vasorelaxation. We have observed that nitrite delivered by the intravenous and inhaled routes reduces arterial stiffness and vasodilates conduit vessels as well as vessels at the arteriolar level (*J Am Coll Cardiol.* 2017;70(2):136-148.), without causing excessive BP reduction or symptomatic hypotension.

The oral formulation of nitrite has been observed to reduce blood pressure. This compound has been administered to patients with obesity and metabolic syndrome, as well as HFpEF and PH as part of [name] ongoing NIH-sponsored studies, and no severe adverse events or symptomatic hypotension have developed following treatment with this oral nitrite formulation ([name], personal communication 2018). We will carefully assess for any adverse

effects that could be related to excessive BP reduction in the study as outlined below in the protocol.

Mechanism of Action: Inorganic sodium nitrite is an intrinsic vasodilator that is converted in blood and tissues to nitric oxide (NO). Endogenous NO₂⁻ represents the body's largest reservoir of NO which results in vasodilation and may improve ventricular diastolic compliance.

Dosage: AIR001 solution for nebulization. The dose of 80mg/ml is administered through a specialized nebulizer device. The oral dose of 40 mg is administered as a capsule, administered three times daily (same as the inhaled formulation).

Metabolism: AIR001 is rapidly absorbed through the alveolar-capillary interface, achieving peak concentrations in less than 5 minutes. Oral nitrite is rapidly absorbed through the alimentary tract, achieving peak levels at 30 minutes. NO₂⁻ is elevated in plasma following both routes of administration and is rapidly converted to NO in areas of low oxygen tension.

Interactions and Contraindications: There are no known drug interactions. NO₂⁻ is not a substrate or inhibitor for hepatic cytochrome p-450 enzymes. Nebulized inhaled nitrite (NO₂⁻) should not be used with other NO donors (e.g. organic nitrates, nitroprusside) to minimize risk of hypotension, and these are listed as exclusion criteria for safety. A drug-drug interaction study with sildenafil dosed at 20mg three times daily did not show a pharmacodynamic interaction, but in this study patients treated with phosphodiesterase inhibitors will be excluded.

Adverse Effects: The most frequent reported adverse effects of AIR001 used in Stage 1 are cough, headache, and dizziness. These effects were reported as mild to moderate intensity and rarely result in discontinuation of medication.

In a Phase 2 study of oral nitrite therapy in older heart failure patients, [name] and colleagues found a higher propensity for hypotension in subjects aged > 70 years with heart failure compared to healthy controls. Two research subjects enrolled in this study were withdrawn by Investigator due to hypotension. In all other studies, oral nitrite and nitrate are generally safe and well tolerated, and all AEs thought to be related to nitrite and nitrate were mild to moderate in severity, and were all resolved with or without minor treatments. No drug related SAEs have been observed in all of the protocols. In sum, the number and nature of anticipated AEs are expected.

The most frequent expected adverse effects with oral nitrite are dry mouth (infrequent), and nausea/abdominal pain/methemoglobinemia/flushing/headache/dizziness (rare).

Abuse Potential: No risk for abuse of AIR001 has been demonstrated.

Pregnancy Risk: Although nitrite exists widely in nature and human ingestion occurs daily in foodstuffs and through water sources, no human data exist on the safety of administration of nitrite during pregnancy or lactation. AIR001 and oral nitrite should not be administered to women who are pregnant or lactating. Effective contraceptive measures should be utilized by women of child-bearing potential who receive either form of nitrite. Given the ubiquitous nature

of nitrite in the environment and the short half-life of AIR001, prolonged contraceptive use after ceasing AIR001 inhalational use is unnecessary, and should be predicated on the clinical judgment of the subject's clinician.

2 Study Objectives

Aim 1: Determine whether treatment with NO₂⁻ in addition to ET for 12 weeks improves exercise capacity and hemodynamic reserve in HFpEF. Expired gas analysis, inert gas (C₂H₂) rebreathe, and echocardiography will be performed during rest and exercise to measure oxygen consumption (VO₂), CO, and hemodynamics before and after completion of 12 weeks of ET with NO₂⁻ vs ET with inhaled placebo.

- Our **primary hypothesis** is that combination therapy with ET and NO₂⁻ will be associated with greater improvement in peak VO₂ compared to ET plus placebo. Our **secondary hypotheses** are that ET and NO₂⁻ will lead to greater improvement in CO reserve (CO/VO₂ slope), peak workload, and exercise hemodynamics (lower echocardiography estimated pulmonary artery pressure and E/e' ratio).

[figure not shown]
Aim 2: Determine whether treatment with NO₂⁻ in addition to ET for 12 weeks increases daily activity levels and QOL, and reduces symptoms of effort intolerance during ET. Subjects will use externally worn accelerometer devices to track daily physical activity. Tolerability of ET will be assessed by Borg perceived effort and dyspnea scores. Large and small vessel endothelial function (brachial and digital arteries) and quality of life (QOL) will be assessed.

- Our **primary hypothesis** is that combination of NO₂⁻ and ET will be associated with greater improvement in daily activity levels compared to ET with placebo. Our **secondary hypotheses** are that combination of NO₂⁻ and ET will be associated with improvement in symptoms of dyspnea and fatigue, improved tolerability to ET, enhanced endothelial function and better QOL compared to ET with placebo.

3 Study Design

3.1 General Design

This is a Phase 2 randomized, double-blind, parallel group placebo-controlled trial testing whether inorganic sodium nitrite, as compared to placebo, can enhance the benefits from chronic exercise training (ET) in subjects with HFpEF (see flow diagram below).

Inorganic Nitrite To Amplify the Benefits and Tolerability of Exercise Training In Heart Failure With Preserved Ejection Fraction

Revised 16 Jan 2019

The total duration of the trial is 14 weeks.

Subjects will be screened from the inpatient and outpatient heart failure services and interested qualified subjects will be offered participation. Once consent has been obtained baseline assessment of cardiovascular function and exercise capacity will be performed. All subjects will undergo 12 weeks of ET. Participants will be randomized to receive sodium nitrite 3 times daily or matching placebo 3 times daily during the study period.

In Stage I this was with inhaled medicine for the full 12 weeks of ET. In Stage II, study drug will be administered using an oral preparation for the full 12 weeks. Study subjects will wear accelerometry devices to track daily activity levels at home.

At the Screening visit, during consent, subjects will be given the option to participate in an optional MRI sub-study where they will be asked to complete 2 Magnetic Resonance Imaging (MRI) scans. One scan will be completed prior to or as close as possible to the beginning of cardiac rehabilitation, the other within 2 weeks of completing week 12 of ET (for Stage II). A hematocrit will need to be obtained prior to the MRI if not already drawn within the past 30 days. We will evaluate adipose tissue content and cardiac structure and function. We will determine whether these variables relate to exercise capacity/intolerance in participants, and evaluate how they change with ET with or without nitrite. Subjects will be excluded from this optional substudy if they have contraindications to MRI including aneurysm clips, cardiac pacemakers, internal defibrillators, severe claustrophobia and pregnancy. Women of childbearing potential will undergo a urine pregnancy test; positive test results will yield exclusion from study participation. Patients will be excluded for contraindications to gadolinium-based MRI contrast material, namely glomerular filtration rate less than or equal to 30ml/min.

The MRI scans will be performed on a clinical scanner or at the Center for Advanced Imaging Research in the Opus building. Patients will have ECG leads placed, as is done for cardiac MRI examinations. In some patients this may require shaving the chest for lead placement. Prior to scanning a peripheral intravenous (IV) line will be placed. Patients may be scanned prone and/or supine. The examination will last approximately one hour. Intravenous contrast material (gadolinium) will be used. Subjects will receive \$25/scan for participating in this MRI sub-study part of the main study.

Also at the screening visit, during consent, subjects will be given the option to participate in an optional muscle biopsy where they will be asked to complete 2 muscle biopsies. One biopsy will be completed prior to or as close as possible to the beginning of cardiac rehabilitation, the other as close to the end of ET. **The muscle biopsy sample will be collected from the vastus lateralis muscle (outer thigh). Muscle biopsy will be performed with a percutaneous biopsy needle (modified Bergstrom needle).** Local subcutaneous injection of 2% lidocaine buffered with 8.4% sodium bicarbonate will be used for analgesia. All biopsies will be done under sterile conditions with all necessary aseptic precautions. A small incision will be made through the skin and fascia. After the biopsy, pressure will be held over the incision until hemostasis is achieved. The incision is closed with sterile strips, gauze and an Ace wrap. Risks of this procedure include hematoma, infection, and pain. Hematoma likelihood is minimized by holding pressure after the biopsy to ensure hemostasis, followed by a pressure dressing. The risk of infection is minimized by using sterile surgical techniques. Pain is managed by local analgesia during the procedure and Tylenol following the procedure. Subjects will receive \$50/biopsy for participating.

At the conclusion of the main trial, subjects will be offered participation in an optional ancillary study where they will be randomized to standard care or behavioral/motivation intervention (once weekly visits with co-investigator +2 phone calls per week) to evaluate durability of ET effects. For subjects participating in this component of the study, there will be one final visit 8-10 weeks following the final study visit where QOL assessment, Borg symptom severity (effort and dyspnea scores) will be recorded during standardized exercise training at a common objective workload, 2 mph on treadmill at 2° grade for 5 minutes and accelerometry data will be obtained (post trial intervention).

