3.3 Secondary Study Endpoints

Cardiac output reserve, peak exercise workload, rest and exercise hemodynamics assessed by echocardiography, Borg dyspnea and fatigue scores recorded during ET, endothelial function assessed by tonometry, QOL assessed by the Kansas City Cardiomyopathy Questionnaire and body composition assessed by dual energy X-ray absorptiometry (DEXA). Cardiac structure and function will be assessed by cardiac MRI and adipose content will be assessed by MRI in subjects participating in the optional MRI substudy. The muscle biopsy will tell us about what improvements we see in the leg muscles, and specifically in the mitochondria of leg muscles.

There will be ancillary trial endpoints to assess QOL, Borg symptom scores, DEXA, AXM data, and exercise capacity following completion of the main trial, comparing subjects randomized to usual care or behavioral/motivation intervention.

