4.1 Inclusion Criteria

1. Age \geq 40 years
2. Symptoms of dyspnea (II-IV) without evidence of a non-cardiac or ischemic explanation for dyspnea
3. EF of $>$ or $=$ 50% determined on most recent imaging study within the preceding 5 years, with no change in clinical status suggesting potential for deterioration in systolic function
4. One of the following:

- Previous hospitalization for HF with radiographic evidence (pulmonary venous hypertension, vascular congestion, interstitial edema, pleural effusion) of pulmonary congestion **or**

- Catheterization documented elevated filling pressures at rest (PCWP ≥ 15 or LVEDP ≥ 18) or with exercise (PCWP ≥ 25) **or**
- Elevated NT-proBNP (>400 pg/ml) or BNP(>200 pg/ml) **or**
- Echo evidence of diastolic dysfunction/elevated filling pressures manifest by medial E/e' ratio ≥ 15 and/or left atrial enlargement **and** chronic treatment with a diuretic for signs or symptoms of heart failure

5. Heart failure is primary factor limiting activity as indicated by answering # 2 to the following question:

My ability to be active is most limited by:

1. Joint, foot, leg, hip or back pain
2. Shortness of breath and/or fatigue and/or chest pain
3. Unsteadiness or dizziness
4. Lifestyle, weather, or I just don't like to be active

6. No chronic nitrate therapy or not using intermittent sublingual nitroglycerin (requirement for >1 SL nitroglycerin per week).

7. No daily use of phosphodiesterase 5 inhibitors or soluble guanylyl cyclase activators and willing to withhold prn use of phosphodiesterase 5 inhibitors for duration of study

8. Ambulatory (not wheelchair / scooter dependent)

9. Body size allows wearing of the accelerometer belt as confirmed by ability to comfortably fasten the test belt provided for the screening process

10. Willingness to wear the accelerometer belt for the duration of the trial

42 Exclusion Criteria

1. Recent (< 1 month) hospitalization for heart failure
2. Ongoing requirement for PDE5 inhibitor, organic nitrate or soluble guanylyl cyclase activators
3. Hemoglobin (Hgb) < 8.0 g/dl within 30 days prior to randomization
4. GFR < 20 ml/min/1.73 m² within 30 days prior to randomization
5. Systolic blood pressure < 115 mmHg seated or < 90 mmHg standing
6. Resting HR > 110
7. Previous adverse reaction to the study drug which necessitated withdrawal of therapy
8. Significant chronic obstructive pulmonary disease that is a primary contributor to symptoms in the opinion of the investigator

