
Dual Energy X-ray Absorptiometry (DEXA) will be performed at the first and final visit in the primary study, and for subjects participating in the ancillary trial, at the final visit of that component, to measure changes in body composition during the trial.

Magnetic Resonance Imaging (MRI) will be performed in subjects participating in the optional MRI substudy to measure cardiac structure and function as well as stiffness along with quantification of central and peripheral adipose tissue. As part of the MRI examination we will measure intramyocardial fat content using multiecho Dixon water and fat separated imaging with variable projection (VARPRO). We will also measure interstitial myocardial fibrosis by extracellular volume (ECV) using the MOLLI TI mapping sequence. These additional cardiac MRI measurements will be analyzed offline by our external collaborators, from completely de-identified MRI scan data. No personal health information will be included in the scans that are transmitted for external analysis.

Muscle Biopsy

Will be performed in subjects participating in the optional muscle biopsy substudy to tell us about what improvements we see in the leg muscles, and specifically in the mitochondria of leg muscles

Biological Samples

Venous blood samples will be collected at baseline, week 4, 8, and 12 to assess clinical stability (NT-proBNP) and safety (blood methemoglobin levels). Methemoglobin levels will be used as safety markers during the study and will be shared with the DSMB. All female subjects of childbearing potential will undergo a urine pregnancy test at study enrollment and end of study.

7 Statistical Plan

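### The MRI substudy accepts a hematocrit up to 30 days old, so any hematocrit drift between draw and scan passes into extracellular volume (ECV) and its change; a same-day draw would remove this at little cost

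*Combined protocol and SAP*

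**What the plan says.** Section 3.1 of the protocol sets the blood-sampling rule for the optional MRI substudy: "A hematocrit will need to be obtained prior to the MRI if not already drawn within the past 30 days". Each participant has two scans, one around the start of cardiac rehabilitation and one within two weeks of finishing week 12 of training. The same section says of contrast: "Intravenous contrast material (gadolinium) will be used". It says of access: "Prior to scanning a peripheral intravenous (IV) line will be placed".

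The MRI paragraph of the study assessments (section 6.5.3) names the fibrosis measure: "We will also measure interstitial myocardial fibrosis by extracellular volume (ECV) using the MOLLI TI mapping sequence". Section 3.1 makes change an object of the substudy, because the investigators will relate the MRI variables to exercise capacity and "evaluate how they change with ET with or without nitrite".

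The text reviewed does not ask for a same-day hematocrit, does not ask for the interval between draw and scan to be recorded, and does not say which hematocrit enters the ECV calculation. The laboratory panel at screening and weeks 4, 8 and 12 (sections 6.1, 6.3 and 6.4 and the schedule of assessments) lists no hematocrit or blood count.

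**The concern.** Hematocrit is a direct multiplier in ECV, so it should describe the blood in the scanner. A window of up to 30 days lets it describe the blood at another time. Some participants will be on diuretics, and section 5.6 discourages but permits their adjustment during the study. Training may also alter plasma volume. Either could move hematocrit inside the window.

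What is at stake is the precision of the ECV change, in an optional subset for which no precision target is stated. There is also a possible bias in the within-group change if hematocrit shifts with training and an older sample catches only part of the shift.

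**Working it through.** There is no plan figure to reproduce: the protocol gives no sample size, SD or precision for ECV. The main-trial calculation (34 per group) concerns peak VO₂ and does not bear on this point.

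**Inputs from the protocol:** maximum hematocrit age 30 days; two contrast scans; ECV as the fibrosis measure; change over training as an object.

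**Inputs that are assumptions:**
- hematocrit H = 0.40 (range 0.35 to 0.45)
- ECV = 30% (range 25% to 35%)
- SD of hematocrit drift at the 30-day ceiling: 2 points (range 1 to 3)
- SD of the ECV change without drift: 2.5 points (range 2 to 4)

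**Step 1: definition.** ECV = (1 - H) × λ, where λ is the ratio of the contrast-induced T1-rate changes in myocardium and blood. This is the standard definition; the protocol does not write it out. At the central values, λ = 0.30 / 0.60 = 0.50.

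**Step 2: effect of one error.** A hematocrit error d shifts ECV by -λ × d, or d / (1 - H) in relative terms.
- 1 point: 0.50 × 1 = 0.5 ECV points (0.01 / 0.60 = 1.7% relative)
- 2 points: 1.0 ECV point (3.3%)
- 3 points: 1.5 ECV points (5.0%)
- 3 points across the ranges: from 3 × 0.25 / 0.65 = 1.15 to 3 × 0.35 / 0.55 = 1.91 ECV points

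**Step 3: added variance of the change, one scan with an old value.** Relative increase = (λ × drift SD)² / (change SD)², with drift taken as independent of the true change.

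| Drift SD | ECV error SD | Added variance at change SD 2.5 |
|---|---|---|
| 1 point | 0.5 | 0.25 / 6.25 = 4% |
| 2 points | 1.0 | 1.00 / 6.25 = 16% |
| 3 points | 1.5 | 2.25 / 6.25 = 36% |

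If both scans use old values and the two drifts are independent, these double to 8%, 32% and 72%.

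**Step 4: sensitivity to the change SD.** For one scan, the smallest figure over the assumed ranges is 0.25 / 16 = 1.6% (drift SD 1, change SD 4). The largest is 2.25 / 4 = 56% (drift SD 3, change SD 2).

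**Step 5: noise or bias.** The rule is the same in both arms. Drift unrelated to arm inflates the variance but does not move the expected nitrite-placebo difference. For the within-group change, 30 days is 30 / 7 = 4.3 weeks, so for a scan at weeks 12 to 14 the oldest permitted sample dates from about weeks 8 to 10, while training is still under way. A steady training effect on hematocrit would then be only partly captured. The documents give neither its direction nor its size.

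**The case against.** The strongest reply is that the effect may be negligible and the documents cannot show otherwise. Every magnitude above is assumed. Thirty days is a ceiling: blood is already drawn at Visit 1 and at the Final Visit, and a hematocrit added there could be days to about two weeks old at the scan. Part of any drift SD may be assay variation, which a same-day sample also carries. Section 7.1 sends secondary-endpoint details to a separate SAP whose text was not available for this review, and the MRI acquisition attachment survives only in part; either could contain sampling instructions. ECV is not named in the aims or in the secondary-endpoint list of section 3.3, which reads "Cardiac structure and function will be assessed by cardiac MRI and adipose content will be assessed by MRI in subjects participating in the optional MRI". These points stand. They limit the size and importance of the finding, but the 30-day rule still permits an avoidable error.

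Three stronger readings are tempting and are not supported.
- **The nitrite-placebo comparison is biased.** Treatment is randomized and blinded, one rule covers both arms, and nothing in the documents suggests that drift differs by arm.
- **Baseline values will be systematically older than final ones.** A reader might infer this from the entry criterion "Hemoglobin (Hgb) < 8.0 g/dl within 30 days prior to randomization" (section 4.2) and the lack of a blood count in the later panels. That criterion concerns hemoglobin and is timed to randomization, not to the scan. No document gives the age of the values used at either scan.
- **All participants are on diuretics.** Section 4.1 requires a diuretic under only one of its four qualifying routes.

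**Conclusion.** The point holds as a low-severity design improvement. The rule as written makes the ECV change noisier than it needs to be and leaves room for a partial bias in the within-group change. Under the stated assumptions, one scan with an old value adds about 4% to 36% to the variance of the change at the 30-day ceiling, and less at shorter intervals. This rests on assumed values for hematocrit, ECV, drift SD and change SD, so it illustrates the scale and does not estimate the loss in this trial. The primary analyses of peak VO₂ and accelerometry are untouched, as are the MRI measures of adiposity and cardiac structure and function that do not use hematocrit.

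**What to change.** Replace the 30-day rule in section 3.1 with a requirement to draw hematocrit on the day of each of the two MRI scans, from the IV line already placed for contrast, and to use that value to calculate ECV. If the same-day sample fails, use the nearest available value and flag it, so that the scan's ECV is not lost.

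For scans already done, record the draw-to-scan interval. Keep all scans in the main ECV analysis and add a sensitivity analysis that leaves out those with older hematocrit values.

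The cost is a small laboratory fee per scan, with no added visit or needle stick, and a smaller subset in the sensitivity analysis. No eligibility rule, treatment or primary analysis changes.
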